newly diagnosed clients who are getting accustomed to ART treatment. During the post-intervention period, the team will follow participants and continue MEMS data collection during the participants' regular clinic visits (expected to be every month for the first six months post treatment initiation, and every one-to-three months thereafter) for a period of six months, bringing the total study period to nine months.

Since the long-term goal of the study is viral suppression, viral load data will also be collected during the routine assessment. Viral load tests for treatment initiators are conducted after the first six months of ART initiation, and then switched to 12-month periods as per clinic and Ugandan Ministry of Health guidelines. Survey assessments will be administered at baseline, month three, and month nine for all participants.

It is important to note that the pilot study is being preceded by a formative phase, and succeeded by an adaptation phase, both of which are geared towards collecting qualitative data pertaining to the overall design, feasibility, and acceptability of the interventions. The results of the formative phase will be used to adapt the pilot intervention materials and timeline prior to the intervention administration. The adaptation phase is expected to provide feedback on the mission critical parameters of the interventions, which would be utilized to mold the intervention in preparation for a full-scale randomized controlled trial. Figure 2 gives the timing of study activities.

Study Sites

The study will be performed at the Mildmay, Uganda, an HIV clinic in Kampala, Uganda. This clinic specializes in providing comprehensive HIV and AIDS prevention, care, and treatment services to over 105,000 HIV-infected patients. It offers integrated health services to a diverse population base; of the 15,000 patients served at the main site in Lweeza, 11% are children younger than 18 years, 65% are female, and 100% of patients are on ART. Mildmay also has well-established electronic medical records infrastructure, making it one of the growing number of facilities using electronic medical record systems in Uganda.

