Qualitative analysis will primarily be performed through semi-structured interviews and focus groups with clients, providers, and clinic administrators during the initiation and adaptation phases. The interviews administered during the initiation phase will primarily focus on perceptions of ART pill-taking as an activity of daily life and investigate the range of existing behaviors that could be used as cues (such as eating, daily prayers, or brushing teeth) to refine how INMIND could best support ART adherence routinization. During the adaptation phase, eight focus groups (four among participants in the *Messages* group and four among the participants in the *Incentives* group) will be organized to elicit additional qualitative information on areas of program improvements that may not be captured in the surveys.

All qualitative data will be digitally recorded, translated into English, and uploaded into Dedoose, an analytic software package. Two qualitative researchers will independently read the text and identify all topics covered. A codebook that details the inclusion and exclusion criteria along with typical exemplars for each topic or theme will be developed. Inter-coder reliability (evidenced by

Cronbach's alpha $\alpha \geq 0.70$) will be established until the coders converge on a single, agreed-upon meaning for the thematic area. For each topic, they will identify the range of themes, with attention to those most commonly discussed (i.e., key themes) and least frequently discussed (i.e., outliers). They will produce research reports on specific topics describing the range, central tendency, and distribution of each theme.

Data Management

All data collected during the course of the study (outside of the consent forms, which will include the participants' name and signature) will only have the existing clinic identifiers as the unique participant identifier. All other identifiable information will be stored separately. Data collection and storage hardware (i.e., tablets and computers) will be password protected and physical storage spaces will have a locking mechanism for security. All physical storage spaces will be located at the Mildmay RAND office in Kampala with access granted only to key personnel and the principal investigator (PI). These physical storage spaces will be used to store the consent forms and other physical tracking documentation.

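### Cronbach's alpha of at least 0.70 is the only measured evidence of inter-coder reliability, and with two coders it can be met at only moderate agreement on the codes

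*Combined protocol and SAP*

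**What the plan says.** The Qualitative Analysis section covers semi-structured interviews and focus groups in the initiation and adaptation phases, including eight focus groups split equally between the Messages and Incentives arms. On coding it says: "Two qualitative researchers will independently read the text and identify all topics covered". Then: "A codebook that details the inclusion and exclusion criteria along with typical exemplars for each topic or theme will be developed". The quality criterion follows: "Inter-coder reliability (evidenced by" a Cronbach's alpha of 0.70 or more) "will be established until the coders converge on a single, agreed-upon meaning for the thematic area".

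Themes are then sorted by how often they are discussed, into key themes and outliers, and the output is described as follows: "They will produce research reports on specific topics describing the range, central tendency, and distribution of each theme". Study Design gives the use to which this is put: "The adaptation phase is expected to provide feedback on the mission critical parameters of the interventions", in preparation for the full-scale trial.

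No kappa, Krippendorff's alpha or percent agreement is named anywhere. The plan does not say what share of the text is double-coded, what the coding unit is, whether alpha is computed per code or overall, or how disagreements are resolved.

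**The concern.** Topics and themes defined by inclusion and exclusion criteria are nominal codes. The question for such codes is whether two coders put the same code on the same piece of text more often than chance would produce. Cronbach's alpha answers a different question. It is built from the covariance between coders and describes the consistency of their combined score. It makes no direct comparison of code assignments, and when one coder uses a code more often than the other it falls less than an agreement coefficient does.

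A reader who sees 0.70 is likely to read it on an agreement scale, where it would be a stricter standard than it is here. What is at stake is the frequency-based sorting of themes and its contribution to adapting the intervention. If coders differ in how often they apply a code, the boundary between a common and a rare theme is less secure than the reported reliability suggests.

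**Working it through.** The 0.70 cut-off is a chosen criterion, so there is no derived figure to reproduce. The check is what it implies for agreement.

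**Inputs from the Qualitative Analysis section.** Two coders; alpha of at least 0.70; codes that are topics or themes.

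**Assumptions.** Each code is scored present or absent per excerpt, and alpha is computed per code. Code prevalence is not given, so a range is shown.

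**Step 1: correlation implied by the cut-off.** For two coders, standardized alpha = 2r/(1 + r), so r = alpha/(2 − alpha) = 0.70/1.30 = 0.538. This step does not depend on the present/absent assumption.

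**Step 2: equal use of the code.** With equal marginals kappa = r = 0.538. With prevalence p, joint coding is p² + 0.538·p(1 − p).

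| Prevalence | Raw agreement | Share of one coder's marked excerpts also marked by the other |
|---|---|---|
| 50% | 76.9% | 76.9% |
| 20% | 85.2% | 63.1% |
| 10% | 91.7% | 58.5% |

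In counts, take 100 excerpts: both coders 38, only A 12, only B 11, neither 39. Covariance = 0.38 − 0.50 × 0.49 = 0.135, and the variances sum to 0.25 + 0.2499 = 0.4999. Alpha = 4 × 0.135/(0.4999 + 0.27) = 0.701. Agreement is 0.77 and chance agreement 0.50, so kappa = 0.27/0.50 = 0.54. The code passes with 23 excerpts coded differently.

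**Step 3: unequal use.** For two coders, raw alpha = 4c/(vA + vB + 2c), where c is the covariance and vA, vB are the variances. Kappa = (observed − chance agreement)/(1 − chance agreement). In the rows below, every excerpt marked by B is also marked by A.

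| Use by A / B | c | vA + vB | Alpha | Observed / chance agreement | Kappa |
|---|---|---|---|---|---|
| 65% / 35% | 0.1225 | 0.455 | 0.700, passes | 0.70 / 0.455 | 0.45 |
| 50% / 25% | 0.125 | 0.4375 | 0.727, passes | 0.75 / 0.50 | 0.50 |
| 20% / 10% | 0.08 | 0.25 | 0.780, passes | 0.90 / 0.74 | 0.62 |
| 10% / 5% | 0.045 | 0.1375 | 0.791, passes | 0.95 / 0.86 | 0.64 |
| 60% / 30% | 0.12 | 0.45 | 0.696, fails | 0.70 / 0.46 | 0.44 |

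A search over two-by-two tables (cells in steps of 1/200, each coder's use between 5% and 95%) found 0.45, the first row, as the lowest kappa that still meets alpha of 0.70.

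**Step 4: what 0.70 on an agreement scale would require.** With equal marginals, kappa 0.70 corresponds to alpha = 1.40/1.70 = 0.82.

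**The case against.** The strongest reply is that alpha is not the whole rule. It is the evidence given in parentheses; the work continues until the coders share one meaning for each thematic area. That stands as a real mitigation. It concerns what a theme means, though, and it is not a measurement of whether the two coders then mark the same excerpts. Alpha remains the only number attached to the step.

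A reader might infer that alpha ignores unequal code use altogether. For present/absent codes this is not so. Halving one coder's use lowers alpha, and the 60%/30% row above fails even with perfect nesting. The 50%/25% case also fails if one of B's 25 marks per 100 excerpts falls outside A's: c = 0.24 − 0.125 = 0.115 and alpha = 0.46/0.6675 = 0.689. Only on an ordered score with a constant shift would alpha miss the difference completely, and the plan describes no such score. The supportable claim is that the penalty is too weak.

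A reader might also infer that the feasibility and acceptability conclusions depend on this statistic. They do so only in part. The Outcomes section lists retention, visit attendance and survey responses first, with focus groups as a supplement, and Statistical Methods and Analyses relies on summaries of self-reported measures. Moreover, a coder who applied every code proportionately less often would leave the ranking of themes unchanged, and the plan does not say that each coder's counts are reported separately.

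Finally, another alpha-type agreement coefficient, such as Krippendorff's, may have been intended. The text says Cronbach's, so a correction would be needed in that case too.

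**Conclusion.** The point holds as a minor one. The only measured criterion for inter-coder reliability is a consistency index, and at two coders its cut-off can be met with kappa of about 0.54 when codes are used equally often and about 0.45 at 65% versus 35% use. In the nested half-frequency examples that pass, kappa is about 0.50 (50% versus 25%) to 0.62 (20% versus 10%), and slightly higher, 0.64, at 10% versus 5%. These kappa values rest on present/absent coding per excerpt and on illustrative prevalences; the correlation of 0.538 does not.

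The consequence is limited to the qualitative themes: their classification as key or outlying, and their input to the adaptation phase. Nothing here bears on the MEMS adherence and routinization outcomes, retention in care, viral suppression or the sample size. The documents also do not show that the coding is in fact poor, only that the stated criterion would not reveal it if agreement were moderate.

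**What to change.** Replace Cronbach's alpha with Cohen's kappa or Krippendorff's alpha for nominal data, computed per code on the double-coded text and reported with raw agreement. State the coding unit, the share of text that is double-coded and how disagreements are resolved. Keep the convergence step as it is.

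If 0.70 is retained as the cut-off, say openly that it is stricter than the present rule, since it corresponds to alpha of about 0.82 with equal marginals. For rare codes, which will include some of the outlying themes, kappa is unstable and should be read alongside raw agreement rather than used alone as pass or fail.

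No new data collection is needed as long as independently double-coded text exists; the plan does not state how much there will be. The cost is that some codes may need another round of codebook revision and recoding. The Results section reports data collection complete and analyses ongoing, so that work would fall within the analysis stage.

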The MEMS caps will be used to assess the primary outcome measures – mean monthly adherence during intervention and post-intervention and a novel adherence measure assessing the timeliness of adherence during the intervention and post-intervention periods. The caps will be distributed to all participants regardless of their group assignment so as to avoid any spurious intervention effects associated with the cap use. The data captured by these caps will be downloaded at each clinic visit using a MEMS cap reader that will be connected to a study computer, and we will use these data to construct our participant-day-level measures of ART medication adherence.

The study coordinator will assist the patient with dispensing their medication into a bottle we provide with an attached MEMS cap, or, if preferred by the patient, they can put the MEMS cap

on the medication bottle provided by the clinic. We will monitor adherence to only one daily dose of antiretroviral medication as studies show that rates of adherence do not differ significantly across medications taken by an individual patient [49]. All participants will be asked to use their MEMS cap continuously throughout the study and return with the cap and their pill bottle for each clinic visit. Participants will be informed that the cap records when the bottle is opened. They will also be informed that these data will not be shared with clinicians.

TIMEPOINT	Enrolment	Allocation	Months								
			Post-allocation			Post-Intervention/Closeout					
			1	2	3	4	5	6	7	8	9
ENROLMENT:											
Eligibility screen	X										
Informed consent	X										
MEMS-Cap Given	X										
Allocation		X									
INTERVENTIONS:											
T1: Messages		X		↔							
T2: Incentives		X		↔							
ASSESSMENTS:											
MEMS-Cap Measured Adherence		X		↔							
Participant Surveys		X		X						X	
Viral Load		X		X							X

Figure 2: Schedule of enrolment, interventions, and assessments (SPIRIT Figure)

Study Timeline

Recruitment

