The fourth outcome will be calculated using the same procedures as *Outcome 3*. However, the data from which the measure will be assessed will be collected during the post-intervention period.

The team will also assess two secondary efficacy measures, as described below:

Secondary Outcome 1: Retention in care

Retention in care is an important metric of treatment adherence. Failure to remain in care is a commonly observed problem for treatment initiators. To assess how well participants will continue to remain in care, Mildmay electronic records will be used to evaluate the number of study participants who fail to observe their regularly scheduled clinic visits. Participants who don't make any clinic visits for six months or more will be considered lost to follow up. The study coordinator will call them using the tracking information collected for the study to inquire about their reason for stopping care at the Mildmay clinic. This outcome will be measured as an indicator of whether the participants are still active clients at the clinic at the end of the nine-month study.

Secondary Outcome 2: Viral Suppression

HIV RNA (viral load) is our final outcome measure. According to the AIDS Clinical Trials Group, virological failure is defined as a confirmed viral load > 200 copies/mL. Below this level, the viral load is considered undetectable. Importantly, this is a reliable biological measure of ART adherence, since strong adherence leads to lower viral load. Given the intervention design, viral load will be an important complementary measure of adherence. The analysis will examine the intervention effects on the likelihood of being virally suppressed at the end of the nine-month study period.

Data Analysis

[Statistical Methods and Analyses](#)

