Feasibility and acceptability will be analyzed using summary statistics derived directly from our self-reported measures. To estimate preliminary efficacy, statistical analyses comparing group-level differences in the secondary and tertiary outcome measures will be performed. An Analysis of Covariance framework will be used to test for group differences in each secondary and tertiary outcome, controlling for the participant characteristics that are found to differentiate the groups at baseline. For analyses of dichotomous variables, such as viral suppression, a non-parametric McNemar's test and an analogous multiple logistic regression will be used to control for covariates to assess group differences. In addition to static comparisons of group means for each outcome at three-month intervals, the longitudinal nature of the data will be leveraged by using repeated measures and time-series techniques. Specifically, a linear mixed model with repeated observations will be fit using maximum likelihood through 'xtmixed' in the

software package Stata to study group-level temporal dynamics in daily measures of the primary and secondary outcomes.

Sample and Effect-size Estimation

We will recruit a total of 150 participants and will assume a 90% retention rate through the 9-month study period. This is a conservative estimate of attrition, as previous research in the same clinic and with a similar population observed only 6% attrition over 12-month study periods [44,48]. Given the study objectives of establishing acceptability, feasibility, and preliminary effectiveness, the targeted sample size may not have the power to detect many of the effects that would be clinically significant. Nonetheless, effect size calculations associated with 80% power (2-tailed test) with regard to the primary outcomes at month nine have been carried out. A recent study conducted at Mildmay suggested that mean ART adherence rates are ~ 75% (SD = 20) as measured by MEMS caps [44]. Using these parameters as estimates of adherence for the control group, and 10% attrition at month nine, a sample size of 150 will provide sufficient power to detect a 9% difference in mean adherence between the pooled intervention groups and the control group (effect size = .47), and a roughly 11% difference in mean adherence between the two intervention groups. This translates to the study being able to detect medium effect sizes.

Qualitative Analysis

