All data collection and on-ground study activities will be carried out by the study team in Uganda. This team will include a team leader, two lead interviewers, and three supporting team members. The design of the data collection instruments and protocols, the quality monitoring of the qualitative and quantitative data, and the data analysis will be carried out by the study team based in the United States (U.S.). Data collected on the ground will be transferred to the US team on a weekly basis through a secure web portal (Kiteworks).

Published material will be free of any personally identifying information. There is no data monitoring committee since the trial was deemed minimal risk. The study team in the U.S. will still perform data monitoring and quality assurance exercises weekly during the nine-month study period.

Handling Missing Data and Attrition

Missing data for some variables will be imputed if a participant remained enrolled in the study. When participants drop out, multiple logistic regression models will be fit to assess whether this dropout is random. If it is not, "nonresponse" weights using logistic regression will be developed to correct for dropout. All analyses will reflect these design effects in the calculation of standard errors and statistical tests of significance.

Results

This pilot study has been funded by the National Institutes of Mental Health in the United States (R34MH122331) and approved by the RAND Human's Subjects Protection Committee (2020-N0632), Mildmay Uganda Research Ethics Committee (0701-2021), as well as the Uganda National Council for Science and Technology (HS128ES). As of February 18, 2022, recruitment was completed. As of August 23, 2023, all the data collection activities were also marked completed; the analyses of the data are ongoing.

Discussion

Expected outcomes

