We hypothesize that our two intervention groups will display higher mean medication adherence and higher routinized medication adherence (i.e., pill-taking within +/- one hour of participants' chosen anchor) during the three-month intervention relative to the control group. After more frequently using their anchoring strategy, we then hypothesize that our two intervention groups will better maintain their mean medication adherence and routinized medication adherence over the six months after the intervention is withdrawn. Finally, we hypothesize that our second treatment group that receives both text message reminders and small incentives for using their anchor during the three-month intervention will more strongly maintain their mean medication adherence and routinized medication adherence during the six-month post-intervention period.

Comparison to prior work

INMIND has a strong scientific premise that addresses a critical knowledge gap in the literature around the design of interventions for establishing and maintaining long-term behavior change. A growing literature in the field of psychology targets long-term behavior change [18,43]; however, most of the intervention methods are one-off interventions that do not support participants during the approximately three-month routinization process [17,20,54,55]. Behavioral economics-based interventions have also had limited efficacy in maintaining long-term behavior change. For example, incentives have successfully changed a range of health behaviors by countering present bias [38–41], including improved ART adherence [42], but these interventions typically show only short-term impact that dissipates after the incentives are withdrawn [38,43]. In our own prior studies, we also found that incentives did not have persistent effects, and only participants who showed timely adherence (an indicator that they potentially

anchored pill-taking to an existing routine) maintained high adherence after the incentives were withdrawn [44].

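### Dropout is handled only by methods that assume leavers' unseen adherence matches that of comparable stayers, and no planned analysis varies that assumption for the persistence outcomes

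*Combined protocol and SAP*

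**What the plan says.** Handling Missing Data and Attrition sets two rules. The first covers people still in the study: "Missing data for some variables will be imputed if a participant remained enrolled in the study". The second covers leavers: "When participants drop out, multiple logistic regression models will be fit to assess whether this dropout is random". If the check finds dropout is not random, nonresponse "weights using logistic regression will be developed to correct for dropout". Statistical Methods and Analyses adds a linear mixed model for daily measures, fitted by maximum likelihood.

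Other sections bear on whether these methods suffice:

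- MEMS-cap procedures: "The data captured by these caps will be downloaded at each clinic visit".
- Secondary Outcome 1: "Retention in care is an important metric of treatment adherence". The same section says that failure to stay in care is common among treatment initiators, and makes active-client status at month nine an outcome.
- Expected outcomes: the intervention groups "will better maintain their mean medication adherence and routinized medication adherence over the six months after the intervention is withdrawn".
- Sample and Effect-size Estimation: "We will recruit a total of 150 participants and will assume a 90% retention rate through the 9-month study period".

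No section plans a tipping-point, bounding or delta-adjusted analysis, or one that counts leavers as non-adherent.

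**The concern.** Weighting represents each leaver by stayers with similar measured characteristics. If the check finds dropout random, leavers drop out of the comparison of means with no adjustment, which is a stronger assumption. With about 15 leavers expected, that check has little power. The mixed model does use a leaver's own observed days, but for later days it too assumes that leavers behave like comparable people who stayed.

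The plan gives reasons to doubt this. Days after a permanent leaver's last cap reading are never seen. The plan treats leaving care as a sign of poor adherence and expects that the intervention might affect it. Missingness may therefore depend on both the outcome and the arm.

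The direction depends on which arm loses more people. If the intervention keeps poor adherers in care, they lower its mean while the control arm's poor adherers vanish, and the contrast is biased against the intervention. If an intervention arm loses more, the bias flatters it. Primary Outcomes 2 and 4 are most exposed because unseen days accumulate over the six months after the intervention. Retention is compared separately and never combined with adherence, so no planned table would show the problem.

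**Working it through.** **Yardstick.** The plan states a detectable difference of 9 points (effect size .47) for pooled intervention versus control, with 80% power, a two-tailed test, SD 20 and 10% attrition. Alpha is not stated. With 0.05 two-sided and 90 versus 45 people: 20 × (1.960 + 0.842) × √(1/90 + 1/45) = 10.2 points. So 9 is not reproduced on that reading. One-sided 0.05 gives 20 × (1.645 + 0.842) × √(1/90 + 1/45) = 9.1. This is a separate matter. I use 9 points below only as the plan's own scale.

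**Check 1: bias of ideal weighting.** From the plan: mean 75, SD 20. Assumed, because the documents give no figures: adherence follows a Beta distribution on 0-100; correlation 0.6 with baseline adherence (Gaussian copula); dropout is logistic in later adherence, with slope 0.03 or 0.05 per point; no treatment effect on adherence; inverse-probability weights on baseline adherence within arm; 400,000 per arm. Leavers then average about 52-64%, and the true contrast is 0. Dropout of 14% in control and 8% in intervention is 7 of 50 plus 8 of 100, which is 15 of 150, the planned 10%.

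Contrasts are intervention minus control, in points. The last two columns score unseen days as 0: (a) leaving spread evenly over the post-intervention period, (b) leaving at its start.

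| Dropout, control vs intervention | Slope | Weighted | (a) | (b) |
|---|---|---|---|---|
| 14% vs 8% | 0.03 | -0.49 | +1.98 | +3.93 |
| 14% vs 8% | 0.05 | -0.90 | +1.79 | +3.61 |
| 16% vs 6% | 0.03 | -0.96 | +3.18 | +6.43 |
| 16% vs 6% | 0.05 | -1.40 | +2.96 | +5.90 |

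- The weighted column is the bias when leavers really are at 52-64%. Repeat runs and coarser weighting classes extend it to about 1.6 points.
- With an assumed correlation of 0.85, standing in for better predictors, the bias falls to about 0.2 to 0.8.
- With equal dropout it is about zero.
- With 11% in intervention and 8% in control (slope 0.03) the sign flips: +0.29 weighted, -0.99 (a), -1.97 (b).

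**Check 2: shift if leavers stop taking pills.** Subtract within a row. The smallest shift is 1.98 + 0.49 = 2.47 and the largest is 6.43 + 0.96 = 7.39, so about 2.5 to 7.5 points. Hand check for (b): 0.06 × 75 = 4.5 and 0.10 × 75 = 7.5.

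**Check 3: when the sign of an observed difference changes.** Let stayers average 75 in control and 75 + D in intervention, with arm dropout d_C and d_T and leavers at adherence a:

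contrast = (1 - d_T)(75 + D) + d_T·a - [(1 - d_C)·75 + d_C·a]

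With 15 leavers of 150 and a = 0:

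- D = 9, equal dropout: 0.90 × 84 - 0.90 × 75 = +8.1.
- D = 9, 2/50 vs 13/100: 0.87 × 84 - 0.96 × 75 = +1.08.
- D = 9, 1/50 vs 14/100: 0.86 × 84 - 0.98 × 75 = -1.26. If dropout is unrelated to arm, at most one control leaver among 15 has a chance of 1.5% (hypergeometric).
- D = 5, 3/50 vs 12/100: 0.88 × 80 - 0.94 × 75 = -0.1.
- D = 3, same split: 0.88 × 78 - 0.94 × 75 = -1.86. At most three control leavers has a chance of 19.6%.

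With a = 37.5, D = 9 never reverses and D = 5 needs 1/50 vs 14/100 (-0.2). With a = 60, no reversal occurs for D of 3 or more. With 6% attrition (9 leavers) and a = 0, D = 9 never reverses: the lowest value is 0.91 × 84 - 75 = +1.44.

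**The case against.** A reader might infer that the planned method itself reverses the sign of the adherence contrast. The documents do not support that. With leavers at 52-64%, the error of weighting is the 0.5 to 1.6 points above. The opposite-signed columns arise only when those same people are rescored to 0, which is a different assumption about leavers. The documents give no adherence figure for leavers, and leaving the study is neither leaving care nor zero adherence.

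A reader might also infer that imputation credits people who left care with stayers' adherence. The plan limits imputation to people still enrolled. What remains is that enrolled is not defined, so someone who has stopped attending but is not yet declared lost could have cap data imputed.

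Other points stand in part:

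- Weights use comparable stayers, not the plain stayer mean. The mixed model uses a leaver's own observed days, and monthly readings during the intervention could improve prediction. Caps record continuously, so someone who returns late fills their own gap.
- Unequal dropout is an assumption. Earlier studies are cited with about 5-6% attrition and no difference by arm is given. The plan does create one arm-specific loss: people whose text registration cannot be confirmed are unenrolled, which can happen only in the two intervention arms. A failed registration does not by itself imply low adherence.
- This is a pilot seeking preliminary efficacy, and retention is reported separately.

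These points limit the size of the problem. None of them supplies an analysis that varies the assumption.

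**Conclusion.** The gap is real and moderate. Every planned treatment of dropout for Primary Outcomes 1-4 assumes that leavers resemble comparable stayers, and nothing tests this. With moderate adherence among leavers and unequal dropout, the bias is small beside 9 points. With leavers who stop treatment, it is large enough to decide the direction of a 3- to 5-point effect under a split such as 6% versus 12%. It would not overturn a 9-point effect unless nearly all leavers came from the intervention arms. These sizes rest on the assumed dropout splits, leaver adherence and correlation, not on trial data. The practical consequence is that a modest persistence effect, or a null result, could not be interpreted from the planned analyses alone.

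**What to change.** Keep the planned analysis as the main one and add one stated sensitivity analysis in all randomised participants, for Primary Outcomes 2 and 4, and for 1 and 3 where days are missing:

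- Use every observed cap day. For participants not known to be in care elsewhere, set adherence on unobserved days after the last cap reading to values from 0% up to the observed mean, varied separately by arm.
- Identify these participants by last cap reading. The six-month lost-to-follow-up rule would miss someone who left midway through the post-intervention period, because that person has not yet met it at month nine.
- Report dropout by arm and reason, and the values at which the conclusion changes.
- Attach no pass/fail robustness rule. Requiring one direction over 0-75% by arm would, with balanced 10% dropout, need 0.9 × (75 + D) > 75. Any stayer difference below 8.3 points would fail.
- Reword the promise of a correction so that it claims only adjustment for dropout related to observed characteristics.

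The Results section says data collection is complete and analysis is ongoing, so the addition should be dated. The cost is a few lines of text and one table, built from cap data, clinic records and the calls already planned to people lost to follow-up. The downside is that a persistence effect may have to be described as sensitive to dropout.
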